## SECONDARY ENDPOINT

#### Efficacy

Change in LVEF from baseline to day 90 post initial infusion. After the crossover phase all patients will be evaluated for change from the new baseline (day 90 after the initial phase) to day 90 post new infusion.

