#### 4 STUDY DESIGN

#### 4.1 Description of the Study

This is a Phase IIa, single-blind, placebo-controlled, crossover, multi-center, randomized study in subjects with N-IHF. Within 3 ±2 days all study participants who meet the eligibility criteria will receive the treatment.

The study will enroll a minimum of 20 subjects and will consist of 2 cohorts. Enrolled subjects will be randomized at 1:1 into an experimental group (n=10), or a placebo group (n=10). Subjects in the experimental group will receive 1.5 million cells per kg and subjects in the placebo group will receive 1 mL/kg LRS. At 90 days the two groups will change arms and the placebo group will receive 1.5 million cells per kg and the initially treated group will receive a Lactated Ringer's Solution (LRS) at a volume of 1 mL/kg.

After discharge, subjects will have safety evaluations per Appendix A. Adverse events, concomitant medications, and assessments will be recorded at each follow-up visit. Complete examinations will be used to assess disability and functional status at baseline (prior to treatment), and at the visits scheduled at 30, 60, and 90, after the initial administration. The same process will be followed at visits scheduled at 30, 60, and 90 days after the new administration (crossover phase). A baseline magnetic resonance imaging (MRI) with delayed contrast enhancement and T2 imaging, as well as a full 2D and Doppler transthoracic echocardiography with speckle-tracking will be performed at baseline and at specific time points during follow-up. All performed MRIs will be assessed in a blinded core lab.

Subjects will continue all of their regular medications unless contraindicated. Subjects may be administered beta-blockers, ACE inhibitors or angiotensin receptors blockers, mineralocorticoid receptor antagonists, statin agents, or other medications, as tolerated. Protocol: STEM-104-M-CHF 16 19FEB2014

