## SECONDARY ENDPOINT

## Efficacy

Change in LVEF from baseline to day 90 post-initial infusion. After the crossover phase all patients will be evaluated for change from the new baseline (day 90 after the initial phase) to day 90 post new infusion

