## Day 90 (±7) days post initial infusion, day of crossover infusion)

- Measure and record vital signs
- Final Formulation Skin Test. Performed prior to infusion (Appendix C)
- 12-lead ECG
- Pulse Oximetry
- 24 hour Holter ECG monitoring or ACD assessment
- Record the composite of all-cause mortality, admission for worsening HF and all-cause admissions, and concomitant medication use
- Physical and cardiac examination
- Clinical labs: serum chemistry including BUN & creatinine, CBC with diff, LFT's, total protein and albumin,
- Cardiac biomarkers (CK and CK-MB fraction, troponin I)
- Serum/plasma stored for VEGF, FGF, NT-proBNP, troponin
- Draw and store blood samples for IgA, IgE, IgG, IgM and for Lymphocyte Proliferation Panel

- Kansas City Cardiomyopathy Questionnaire (KCCQ)
- New York Heart Association (NYHA) Classification
- Spirometry/DLCO
- 6 minute walk test
- Cardiac MRI, with delayed contrast enhancement
- Full 2D and Doppler transthoracic echocardiography with speckle-tracking
- Pregnancy test for women of childbearing potential

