#### 9.1 Randomization

Once eligibility and consent are confirmed, participants will be randomly assigned to the experimental or placebo group in a 1:1 allocation ratio, stratified by site. At 90 days the two groups will change arms and the placebo group will receive the stem cell infusion and the initially treated group will receive a LRS at a volume of 1 mL/kg.

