#### 9.3 Efficacy Analyses

The actual score and calculated change from baseline for each outcome measure (LV end diastolic volume, LVEF, Ventricular Arrhythmias, Kansas City Cardiomyopathy Questionnaire and the New York Heart Association Classification) will be tabulated for each scheduled assessment visit. Summary statistics will consist of sample size (N), means, standard deviations, medians, and minimum and maximum values will be used to summarize the data. Subjects who receive complete dose of investigational product or LRS and have post-administration assessments will be used as the efficacy evaluable population for statistical analysis.

The primary efficacy endpoint will be evaluated and is the change from baseline to Day 90, and 180 on the above measures. For each of the efficacy endpoints, a mixed-effect repeated measures (MMRM) analysis will be conducted to determine if the change from baseline to six months in the experimental group is different than that for the placebo group. The model will include the change in endpoint score from baseline to each post-baseline visit as the outcome variable, the baseline score, time, study site, treatment group and time-by-treatment interaction as fixed effects, and participant as a random effect. An unstructured covariance matrix will be used to model the within-subject variance-covariance errors. Time (0, 30d, 90d, and 180d) will be treated as a categorical variable in the analysis. The mixed model seamlessly accommodates different times of measurement as well as missed measurement and data from participants who are lost to follow up.

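### Section 9.3 places its only named efficacy comparison at six months, when both groups are due to have had cells, so it cannot show cells against placebo

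*Combined protocol and SAP*

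**What the plan says.** Section 9.3 gives the efficacy endpoint as follows: "The primary efficacy endpoint will be evaluated and is the change from baseline to Day 90, and 180 on the above measures". The one between-group efficacy test it then states is a mixed model for repeated measures, run "to determine if the change from baseline to six months in the experimental group is different than that for the placebo group". The model contains baseline score, time, site, treatment group and time-by-treatment, with participant as a random effect. It has no period, sequence or carry-over term. On the time factor: "Time (0, 30d, 90d, and 180d) will be treated as a categorical variable in the analysis".

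The design is a crossover. Section 4.1: "At 90 days the two groups will change arms and the placebo group will receive 1.5 million cells per kg". Section 9.1 repeats that "the placebo group will receive the stem cell infusion and the initially treated group will receive a LRS". Section 7.3 labels the Day 90 visit "post initial infusion, day of crossover infusion", so there is no washout.

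Section 4.2 defines the secondary endpoint by period. The first part is "Change in LVEF from baseline to day 90 post-initial infusion"; after the crossover, subjects are "evaluated for change from the new baseline (day 90 after the initial phase) to day 90 post new infusion".

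**The concern.** The six-month sentence reads as if the trial were a parallel-group study with an untreated control up to Day 180. No such control exists at that visit. The comparison sets patients 180 days after cells against patients 90 days after cells, and calls the second group placebo.

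Followed as written, a product that works and keeps working would be expected to show no difference. A product that works and fades would look worse than placebo. A positive result would show growth of the effect after Day 90, which is a different question. The sentence also does not analyse the Period 2 endpoint of Section 4.2, which is measured from a new Day 90 baseline.

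**Working it through.** The documents give no effect size, SD, significance level or power for efficacy, so there is no planned figure to reproduce. The check is the expected value of the named contrast.

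**Set-up.** Let e90 and e180 be the effects of cells on change from the original baseline, 90 and 180 days after infusion, and let r = e180/e90. Assume additive effects that depend only on time since cells, groups coded as first randomised, and a complete crossover. Time trends cancel between randomised groups.

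- Day 90: e90 − 0 = e90.
- Day 180: e180 − e90 = e90(r − 1).
- Day 180 recoded by current infusion: e90(1 − r).

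**Illustrative inputs.** Section 2.7 reports mean LVEF after STEMI, with open controls. With cells it was 42.1, 52.3 and 54.7 at baseline, 3 and 6 months; in controls it was 42.3, 42.8 and 46.1.

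- e90 = (52.3 − 42.1) − (42.8 − 42.3) = 10.2 − 0.5 = 9.7
- e180 = (54.7 − 42.1) − (46.1 − 42.3) = 12.6 − 3.8 = 8.8
- r = 8.8/9.7 = 0.907
- Named contrast = 8.8 − 9.7 = −0.9

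Holding e90 at 9.7 and varying r:

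| r | Day 90 | Day 180 as named | Day 180 by current infusion |
|---|---|---|---|
| 1.5 | +9.7 | +4.85 | −4.85 |
| 1 | +9.7 | 0 | 0 |
| 0.907 | +9.7 | −0.9 | +0.9 |
| 0.5 | +9.7 | −4.85 | +4.85 |
| 0 | +9.7 | −9.7 | +9.7 |

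The negative values in the third column come from the labels. They are not evidence that cells do harm.

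**Chance of a significant result.** Noncentral t, 10 per group, 18 df, two-sided test, r = 0.907. The SDs of change (6, 8, 10) and both levels are assumed.

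| Level | Day 90, for cells | Day 180, for the group labelled experimental | Day 180, against it |
|---|---|---|---|
| 5% | 93 / 73 / 54% | 1.1 / 1.4 / 1.6% | 5.0 / 4.3 / 3.8% |
| 10% | 97 / 83 / 67% | 2.5 / 3.0 / 3.3% | 9.3 / 8.0 / 7.3% |

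**Simulation of the planned model.** 4,000 replicates, change at Days 90 and 180, unstructured covariance, two-sided 5%; assumed between-subject SD 6 and measurement SD 4. With e90 = 9.7 and e180 = 8.8, Day 90 averages +9.7 and is significant for cells in 97%. Day 180 averages −0.9, with 1.1% significant for and 5.2% against the group labelled experimental. Adding an assumed within-subject drift of SD 5 per period gives 78.5% at Day 90, and 1.6% for and 3.8% against at Day 180.

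With a true 90-day effect of 5 points and no drift, Day 90 is significant in 51–53%. Day 180 behaves as follows:

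| r | Mean Day 180 contrast | Significant for | Significant against |
|---|---|---|---|
| 1.5 | +2.5 | 16.1% | 0.2% |
| 1 | 0.0 | 2.4% | 2.4% |
| 0.5 | −2.4 | 0.2% | 15.7% |
| 0 | −5.0 | 0.0% | 50.6% |

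A separate simulation, using covariance analysis visit by visit with SDs of change of 5, 7 and 10, gave the same pattern.

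**Time levels.** Change from baseline at time 0 is zero by definition. Section 7.1 and Appendix A schedule MRI and echocardiography at screening, Day 90 and Day 180 only. KCCQ, NYHA class and Holter are also collected at Days 30, 60, 120 and 150. The list 0, 30, 90, 180 fits neither set.

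**The case against.** The strongest reply is that Section 9.3 lists Day 90 as an endpoint time, runs the model for each efficacy endpoint and includes time-by-treatment. The valid Day 90 contrast therefore comes out of the same fit, and the six-month clause may be loose drafting. It is true that the contrast is available. But the stated test is tied to six months, and no section names Day 90 as the between-group test.

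Second, Section 9 tabulates outcomes by treatment actually received, and coding by current infusion would remove the sign reversal when the effect wanes. That sentence concerns tables, and the recoded contrast is still zero at r = 1. If the Day 90 baseline of Section 4.2 were used as well, the Period 2 contrast would be e90(2 − r), which is right at r = 1. Section 9.3 describes neither step, and a change measured to six months does not suggest them.

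Third, safety is primary, Section 9 calls the analyses descriptive and promises a detailed analysis plan, and Section 9.4 calls the trial exploratory. This stands and limits the consequence. It does not make the stated comparison valid.

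Fourth, the numbers borrow from another disease and use assumed SDs and levels. In the one scenario taken from the documents the effect largely persists, so the likely outcome is a null result; strong reversal needs smaller values of r that no document supports. That is fair, and the conclusion rests on the algebra rather than on those figures.

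**Conclusion.** The concern holds: the comparison is wrong as written. The only efficacy comparison that Section 9.3 names has expectation e90(r − 1). It is zero when the effect lasts, reversed when it wanes and positive only when it grows. It equals a cells-versus-LRS comparison, with the sign reversed, only if nothing carries over (r = 0).

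This assumes additive effects that depend on time since infusion, the same 90-day effect in either period, coding by first allocation and crossover as planned. Subjects who miss the crossover cells would move the contrast back towards cells against no cells. The error is confined to the six-month test; the Day 90 contrast in the same model is sound.

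**What to change.** 1. Name the randomised Period 1 contrast as the efficacy comparison: change from baseline to Day 90, adjusted for baseline and site, with LVEF first as in Section 4.2. State that the Day 90 measures precede the second infusion. Section 7.1 implies this for MRI by calling that scan a new baseline, and Appendix A says it for the Holter, but neither states it outright for MRI or echocardiography.
2. Stop presenting Day 180 as cells against placebo. Report it descriptively by sequence, or label it a durability contrast (180 against 90 days after cells).
3. Drop time 0 and set the Period 1 time levels by endpoint: Day 90 for LVEF and LV end-diastolic volume; Days 30, 60 and 90 for KCCQ, NYHA class and ventricular arrhythmias.
4. Optionally, add a supportive two-period model with period-specific baselines and its carry-over assumption stated. It averages e90 from Period 1 and e90(2 − r) from Period 2, giving e90(3 − r)/2, which is unbiased only at r = 1.

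This is a change of wording and needs no new visits or data. The cost is that the main comparison leaves out the placebo-first group's data after cells. The standard error is about 2.4 LVEF points, against about 2.2 for the joint model, under the assumed SDs of 6 and 4. The joint model's smaller error comes with bias when the effect wanes: a true 5 is estimated as 5 × 2.5/2 = 6.25 at r = 0.5 (6.3 in simulation) and 5 × 3/2 = 7.5 at r = 0.

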#### **STUDY DESIGN**

This is a Phase IIa, single blind, placebo-controlled, crossover, multi-center, randomized study in subjects with NIHF. The study will enroll 20 subjects and will consist of 2 cohorts. Enrolled subjects will be randomized at 1:1 into an experimental group (n=10) or a placebo group (n=10), respectively. Subjects in the experimental group will receive 1.5 million cells per kg and subjects in the placebo group will receive 1 mL/kg Lactated Ringer's Solution. At 90 days the two groups will change arms and the placebo group will receive 1.5 million cells per kg and the initially treated group will receive a Lactated Ringer's Solution (LRS) at a volume of 1 mL/kg.

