## Cardiac MRI

- Cardiac MRI with gadolinium contrast will be performed at baseline and after 90 days after initial infusion. After the crossover phase an MRI with gadolinium contrast will be performed at new baseline (day 90 after the initial phase) and after 90 days. MRI sequences will include balanced steady state free precession sequence (b\_SSFP) and a delayed contrast enhanced imaging sequence using IV gadolinium contrast, and T2 imaging. Image analysis will be performed by an experienced central laboratory blinded to the subjects' treatment. Efficacy endpoints evaluated by MRI will include: LV end diastolic volume EDV, LV end systolic volume, ESV, and global Left Ventricular Ejection Fraction, and assessment of T2 images for assessing the tissue status
- End-diastolic and end-systolic endocardial traces from contiguous short axis slices will be used to
  determine end-diastolic and end-systolic left ventricular volumes and ejection fraction. Subjects with
  contraindications (e.g. implanted devices, surgical prosthesis, renal impairment or claustrophobia) will not
  undergo MRI.

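### The MMRM in Section 9.3 contradicts itself: it has a time-0 level for a change-from-baseline outcome, a participant effect on top of an unstructured covariance, and a visit grid that fits none of its measures

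*Combined protocol and SAP*

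**What the plan says.** Everything at issue is in Section 9.3, in the paragraph that sets out the mixed model.

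- Outcome: "The model will include the change in endpoint score from baseline to each post-baseline visit as the outcome variable".
- Fixed effects: "the baseline score, time, study site, treatment group and time-by-treatment interaction as fixed effects".
- Random effect: "participant as a random effect".
- Residual covariance: "An unstructured covariance matrix will be used to model the within-subject variance-covariance errors".
- Time factor: "Time (0, 30d, 90d, and 180d) will be treated as a categorical variable in the analysis".

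The measures named at the start of 9.3 are LV end-diastolic volume, LVEF, ventricular arrhythmias, KCCQ and NYHA class. Section 9 gives no convergence rule, no fallback covariance and no degrees-of-freedom method. The synopsis sets the size: "The study will enroll 20 subjects and will consist of 2 cohorts".

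For imaging, Section 7.1 says: "Cardiac MRI with gadolinium contrast will be performed at baseline and after 90 days after initial infusion". A further scan follows 90 days after the crossover infusion.

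**The concern.** Three parts of the specification do not fit together.

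1. The outcome sentence implies post-baseline rows only, but the time factor includes level 0. A row at time 0 would hold a change of exactly zero for every subject.
2. An unstructured matrix can already represent any within-subject covariance pattern. A participant variance on top has nothing left to describe.
3. One grid of times is prescribed for all measures, although they are collected on different schedules.

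An analyst following the paragraph has to depart from some part of it. Which departure is chosen matters, because some repairs give sound standard errors and others do not. With about 20 subjects, that choice should be fixed before outcomes are seen.

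**Working it through.** The protocol states no SD, correlation, effect size or power for efficacy, so there is no figure of its own to reproduce.

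**Step 1: time 0 under an unstructured matrix.** With the time-0 rows kept, the row and column for time 0 have zero variance and covariance. In one simulated data set (20 subjects; times 0, 90 and 180; 0.001 added to the starting time-0 variance), the REML updates took that variance to 1.5e-4 after 1 iteration and 2.2e-8 after 12. The determinant went towards zero with it. There is no proper solution.

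**Step 2: participant effect plus unstructured.** An unstructured matrix over T times has T(T+1)/2 parameters, and the participant variance adds one. The rank of the map from these parameters to the marginal covariance is:

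| Times | Parameters | Rank |
|---|---|---|
| 2 | 3 + 1 = 4 | 3 |
| 3 | 6 + 1 = 7 | 6 |
| 4 | 10 + 1 = 11 | 10 |

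Exactly one parameter is unidentifiable each time. The marginal model is unchanged, so estimates and standard errors for the fixed effects are not biased by this alone.

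**Step 3: grid against schedule.**

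| Measure | Scheduled after baseline | Mismatch with 30/90/180 |
|---|---|---|
| LVEF, LV end-diastolic volume (MRI and echo in 7.1; Appendix A) | 90, 180 | Day 30 level is empty |
| KCCQ, NYHA (Appendix A) | 30, 60, 90, 120, 150, 180 | 60, 120, 150 have no level |
| KCCQ, NYHA (exploratory endpoints, synopsis and 4.2) | 30, 60, 90, 120, 180 | 60, 120 have no level |
| Arrhythmias by Holter (7.1; Appendix A) | 30, 60, 90, 120, 150, 180 | 60, 120, 150 have no level |

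**Step 4: what a repair does to the standard error.** Suppose the time-0 rows stay and the covariance becomes compound symmetry or a random intercept. The variance is then pooled over T times, one of which contributes zero. With equal variance at the other times, the ratio of model SE to true SE is sqrt((T − 1)/T).

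- LVEF at 0/90/180: sqrt(2/3) = 0.816, so 18.4% too narrow.
- The four listed times: sqrt(3/4) = 0.866, so 13.4% too narrow.

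The formula ignores covariate adjustment, so it was checked by simulation. Assumptions, none from the protocol: 20 subjects, two sites of 10, complete data, correlation between raw values of 0.3 to 0.9, and SD constant or rising 30% over follow-up. There were 1,500 runs per scenario, or 600 for the unstructured fit.

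| Repair | Scenario | Model SE / true SE |
|---|---|---|
| Time-0 rows kept, random intercept | 0/90/180, constant SD | 0.80 to 0.86 |
| Same | 0/30/90/180, constant SD | 0.85 to 0.93 |
| Same | rising SD, Day 180 | 0.78 to 0.85 |
| Same | rising SD, Day 90 | 0.88 to 0.92 |
| Post-baseline rows, random intercept | constant SD | 0.98 to 1.04 |
| Same | rising SD | 0.91 to 1.09 |
| Post-baseline rows, unstructured, no participant effect | constant SD, last visit | 0.98 to 1.01 |

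The first repair therefore gives standard errors 7% to 22% too narrow. The last gives a bias of about 0% to 2%.

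**The case against.** The best defence is that a sensible reading is already in the paragraph. If the outcome exists only at post-baseline visits, there are no time-0 rows, the level drops out, and baseline enters as a covariate. That stands, and it rules out an inference a reader might draw, that the model cannot be fitted at all. The redundant participant effect gives warnings rather than wrong inference. The text still lists level 0, however, and does not say which sentence governs.

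A reader might also infer that the analyst will be forced to change the model after seeing it fail. The opening of Section 9 promises a detailed SAP before data analysis, so there is a planned point for correction.

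A reader might take it that half the KCCQ and NYHA visits are thrown away. On the Appendix A schedule three of six have no level. Under the exploratory endpoint definitions it is two of five. In either case 9.3 still tabulates the measures at each scheduled visit, and limiting a model to fewer visits can be a defensible choice in a small trial. It should be stated as a choice.

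Section 9.3 adds that a mixed model copes with differing measurement times and missed visits. That does not help here: a categorical level with no data is inestimable, and an unlisted visit has no level.

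Finally, safety is primary, Section 9 calls the analyses descriptive, and Section 9.4 calls the study exploratory and unpowered. The Day 180 contrast also needs separate thought because the groups switch at Day 90. These points limit the consequences. They do not remove the inconsistency, since 9.3 uses this model to decide whether the groups differ on every efficacy endpoint.

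**Conclusion.** The specification is internally inconsistent and should be corrected. The singularity (if time-0 rows are kept), the single unidentifiable parameter and the grid mismatch follow from the protocol's own text and need no outside assumption.

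The effect on standard errors is conditional. A reader might infer that the planned analysis carries one known narrowing, close to a fifth, with a matching inflation of type I error. The documents do not support that. They name no fallback, and a figure near a fifth needs an analyst who keeps the structural zeros, adopts compound symmetry or a random intercept, and works on 0/90/180. For that repair the narrowing is about 18% by formula for LVEF, about 13% with the four listed times, and 7% to 22% across the simulated scenarios. It rests on assumed correlations, variance patterns and complete data. A repair that follows the stated outcome definition and keeps the unstructured matrix shows about 0% to 2%.

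**What to change.** Amend 9.3, or settle it in the promised SAP, before data analysis:

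- Remove time 0. Model post-baseline changes only, with baseline as a covariate.
- Set the time levels for each endpoint to the visits at which it is defined and measured: Days 90 and 180 for LVEF and LV volume, and a stated list for KCCQ, NYHA and Holter. Reconcile Day 150 between Appendix A and the exploratory endpoint definitions, and give the reason for any collected visit left out.
- Use an unstructured covariance without the participant random effect, with Kenward-Roger degrees of freedom.
- Name a simpler fallback in advance, on post-baseline rows only, with the rule that triggers it. It is needed for the frequently measured endpoints: six visits require 6 × 7 / 2 = 21 covariance parameters from about 20 subjects. A structure that lets the variance differ by visit deserves consideration, because a plain random intercept was up to 9% off in either direction when the SD rose.

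The cost is wording only, with no change to visits, data collection or sample size. The change is needed however the post-crossover data are handled.
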